# RECORDATI AG, Rare Diseases Branch LCI699-RECAG-NI-0596

Statistical Analysis Plan

objection letter (NOL) will be requested from the patient if still alive. If patient does not send the NOL back to the investigator, the investigator can document a tacit approval from the patient if there is no response after a month of the first shipment of the NOL and after 3 documented contact attempts. For a deceased patient since his/her past treatment with osilodrostat, access after the investigator has checked that this deceased patient did not leave any written document stating his/her refusal to participate in any scientific research.

Investigators will manually review and abstract clinical information from selected patients' medical records and will enter information into the electronic case report form (eCRF) from the date of initiating Osilodrostat through the follow-up period. All data are safeguarded using industry-best security practices to prevent unlawful disclosure and practices are compliant with Title 21 Part 11 policies of the Code of Federal Regulations. The HIMS software used for EDC purposes include password protection and encryption for all transmitted data. The platform will be approved by Recordati prior to study data abstraction or during site selection procedure.

The follow-up period will be variable, from the start of their osilodrostat onset period until the earlier of loss to follow-up, death, the end of the retrospective follow-up period or treatment discontinuation occurs. The patients with a potential follow-up of at least 12 weeks will be part of the primary analysis. The only patients excluded from the primary efficacy analyses will be the ones who started treatment with osilodrostat less than 12 weeks prior to the end of the abstraction period and are still treated with osilodrostat at the end of the abstraction period. These patients will be included only in the analyses of the secondary and exploratory endpoints including safety. The patients who discontinued treatment for any reason or were lost-to-follow up prior to 12 weeks will be considered non-responders for the primary endpoint. The end of study is defined as the last available assessment after treatment initiation for the last patient.

The timing of data collection is summarized in the Figure 1/Table 1.

**Table 1 Data Collection Schedule** 

	Data Collection Points						
Assessment	BL a	Wk 4 b	Wk 8 b	Wk 12 b	Wk 18 b	Wk 24 b	Wk 36 and every 12 wks Until death, loss to F/U or end of patient data collection*
Window period		± 2 wks	± 2 wks	± 4 wks	± 2 wks	± 4 wks	± 4 wks
No Objection Letter c	X						
Inclusion-Exclusion Criteria	X						
Demographics (age, gender)	X						
BMI	X	X	X	X	X	X	X
Clinical (disease) characteristics including date of diagnosis	X						
Medical and surgical history	X						

Project Document Version No.: 4.0; Document Effective Date: 30 October 2023

**CONFIDENTIAL** 

# RECORDATI AG, Rare Diseases Branch LCI699-RECAG-NI-0596

Statistical Analysis Plan

LC1099-RECAG-INI-0390						ى رە ماد	ilisticai Arialysis Piari
CS-Specific Physical Exam Findings (after BMI per every visit)@	X	X	X	X	X	X	X
Vital signs (blood pressure)	X	X	X	X	X	X	X
Electrocardiogram	X	X	X	X	X	X	X
Prior cs treatment	X						
Concomitant medications	X	X	X	X	X	X	X
Osilodrostat initiating dose (date) d	X	X	X	X	X	X	X
Up- and/or down-titration regimen (date) d		X	X	X	X	X	X
Comprehensive Metabolic Panel (CMP&), Complete Blood Count (CBC#), lipids	X	X	X	X	X	X	X
HBA1c	X	X	X	X	X	X	X
Mean urinary free cortisol	X	X	X	X	X	X	X
Morning serum cortisol	X	X	X	X	X	X	X
Plasma Adrenocorticotropic hormone (ACTH), Serum 11-Deoxycortisol, Plasma 11- Deoxycorticosterone, Plasma Aldosterone, Plasma Renin, Total Serum Testosterone or oestradiol (per patient sex), Serum LH, Serum FSH	X	X	X	X	X	X	X
Late night salivary cortisol	X	X	X	X	X	X	X
Adverse event	X	X	X	X	X	X	X
Osilodrostat discontinuation with reason for discontinuation		X	X	X	X	X	Х

- a. At the time of osilodrostat initiation or the closest value within 2 weeks prior to osilodrostat initiation.
- b. Assessments at 4, 8, 12, 18, 24, 36 weeks will be collected, as well as all subsequent follow-up visits (at every 12 weeks until the earlier of loss to follow-up, death, or the end of the retrospective follow-up period or treatment discontinuation) under routine clinical practice, if available. The assessments which occurred closest to each defined visit should be recorded in the CRF, even if these assessments occurred on different dates.
- c. Either the patient has previously signed a general consent for research, or a signed no-objection letter (NOL) will be requested from the patient if still alive. If patient does not send the NOL back to the investigator, the investigator can document a tacit approval from the patient if there is no response after a month of the first shipment of the NOL

Project Document Version No.: 4.0; Document Effective Date: 30 October 2023

CONFIDENTIAL

and after 3 documented contact attempts. For a deceased patient since his/her past treatment with osilodrostat, access after the investigator has checked that this deceased patient did not leave any written document stating his/her refusal to participate in any scientific research.

- d. Osilodrostat initiation dose and up- and/or down-titration regimens (including dates) and reasons for titration will be recorded in the database during the study.
- e. All prior medications taken within 6 months prior to the first dose of Osilodrostat must be collected.
- f. Baseline mean urinary free cortisol data can be collected within 1 month prior to osilodrostat initiation.
- g. Footnote-a is not applicable to the following assessments: prior medications, concomitant medications and mean urinary free cortisol.
- \*End of data collection may be due to earlier of loss-to-follow-up, death, end of retrospective follow-up period or treatment discontinuation.
- \*CBC includes WBC, RBC, Haemoglobin, Haematocrit, MCV, MCH, MCHC, RDW, Platelet Count, MPV and Differential (Absolute and Percent Neutrophils, Lymphocytes, Monocytes, Eosinophils, and Basophils).
- &CMP includes Albumin, Alkaline Phosphatase, ALT, AST, Calcium, Carbon Dioxide, Chloride, Creatinine with GFR Estimated, Glucose, Potassium, Sodium, Total Bilirubin, Total Protein, (Blood) Urea Nitrogen.
- @ For list of CS-specific examination findings, please refer to protocol section 8.3.2.

As this is a descriptive study, the effectiveness and safety endpoints will be summarized descriptively. No formal statistical hypothesis testing will be performed.

Data from an approximately 100 patients meeting the inclusion/exclusion criteria in France will be collected.

# 3.1 Identification of Analysis Population

Patients will be entered into this study only if they meet all of the following inclusion criteria and none of the following exclusion criteria:

#### Inclusion criteria:

- Male and female patients ≥18 years old with diagnosis of CS, except for CD (i.e., an aetiology of adrenal adenoma, adrenocortical carcinoma, adrenal hyperplasia, or ectopic adrenocorticotropic hormone secretion). Patients should have a contemporaneously documented diagnosis of CS as per effective guidelines.
- 2) Patients treated with osilodrostat between April 2019 and study start date (16 December 2022) as part of ATU programme or commercialisation.

#### Exclusion criteria:

- 1) Patients who participated in an interventional clinical trial anytime during the study period.
- 2) Patients with Pseudo-Cushing's syndrome, cyclic CS, or iatrogenic CS.

As this is a retrospective, non-interventional study, no specific withdrawal and replacement criteria are specified.

Project Document Version No.: 4.0; Document Effective Date: 30 October 2023

CONFIDENTIAL

TP-GDO-WW-096-09 Effective Date: 22 Dec 21

Related to: SOP-GDO-WW-019 Page 13 of 31

# 3.2 Enrolled Population

All participants treated with osilodrostat between April 2019 and the study start date (16 December 2022), meeting the inclusion/exclusion criteria and for whom authorizations for getting access to the medical data have been ensured, through the existence of a signed general consent, or requesting a signed NOL, or fulfilling the conditions of a tacit approval or no written document stating they refused any participation to scientific research, will be included.

## 3.3 Primary Analysis Population

#### **ITT Population**

The Intent-to-treat population (ITT) consists of all enrolled participants who, have met all inclusion/exclusion criteria and have received osilodrostat treatment for non-CD CS, with a potential follow-up of at least 12 weeks. The only patients excluded from the primary efficacy analyses will be the ones who started treatment with osilodrostat less than 12 weeks prior to the end of the abstraction period and are still treated with osilodrostat at the end of the abstraction period. These patients will be included only in the analyses of the secondary and exploratory endpoints including safety.

All effectiveness analysis will be performed on the ITT population.

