8.7.3 Analysis Population(s)

The ITT population consists of all enrolled participants who, have met all inclusion/exclusion criteria and have received osilodrostat treatment for non-CD CS, with a potential follow-up of at least 12 weeks. The only patients excluded from the primary efficacy analyses will be the ones who started treatment with osilodrostat less than 12 weeks prior to the end of the abstraction period, and are still treated with osilodrostat at the end of the abstraction period. These patients will be included only in the analyses of the secondary and exploratory endpoints including safety.

Final v2.0 48 of 63 18 April 2023

The Safety population consists of all participants who receive at least one dose of osilodrostat.

All effectiveness analysis will be performed on ITT population. Safety analysis will be performed on the safety population.

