8.9 Limitations of the Research Methods

Due to the observational nature of this retrospective cohort study, conducted under conditions of routine clinical practice, bias is more prone to occur. Consequently, study findings may be subject to limitations in generalizability to the target population in availability of data, and variability in local treatment practices and guidelines.

This study is an observational study and relies on patients' existing medical records available at the time of notification of the protocol to the French Data Hub. Therefore, although all patients will be followed longitudinally using historical medical records, some data points may be missing. However, it is expected that any missing data will be

Final v2.0 54 of 63 18 April 2023

minimal and would not affect the study outcome, or that statistical methods of imputation and/or missingness will mitigate its effect.

Many factors can lead to biased study results. The possible sources of bias are selection bias, inconsistent data collection, measurement error with continuous variables, misclassification with categorical variables, confounding factors, methodical errors, and other errors. A good study plan, a good risk management plan, and the good quality control procedures are the key to reducing, avoiding, correcting predictable problems.

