#### 5.3.2 Analysis of the Primary Endpoint

The mean UFC for a participant at any particular visit is collected in the site. If mean UFC is not available at that visit, the mean UFC will be computed based on two or more individual 24hr UFC specimens at that visit. If there are only one individual 24hr UFC specimen available at that visit, then this one individual 24hr UFC specimen will be considered as mean UFC with the acknowledgement of clinical practice in France where one 24 hours UFC can inform on clinical decision.

The primary endpoint is the number and proportion of participants with mUFC ≤ ULN at 12 weeks will be summarized descriptively along with associated 95% CI. The participants who discontinued treatment prior to 12 weeks for any reason or were lost-to-follow up will be considered non-responders for the primary endpoint. The participants who started treatment with osilodrostat less than 12 weeks prior to the end of the abstraction period and are still treated with osilodrostat at the end of the abstraction period will be excluded from the analysis.

Project Document Version No.: 4.0; Document Effective Date: 30 October 2023

CONFIDENTIAL

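### The ITT definition sorts late starters by start date, the primary exclusion rule sorts them by treatment status, and their place in secondary effectiveness is contradictory

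*SAP*

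**What the plan says.** SAP 3.3 (ITT Population) defines the ITT as enrolled, eligible, treated patients "with a potential follow-up of at least 12 weeks". The next sentence allows one exclusion from the primary analysis and sets two conditions for it. The first is a late first dose, under 12 weeks ahead of the close of abstraction. The second concerns treatment status: "and are still treated with osilodrostat at the end of the abstraction period". The same exclusion stands in SAP 3 (Study Design) and SAP 5.3.2, and in Protocol 8.1, 8.7.3 and 8.7.8.

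SAP 5.3.2 adds: "The participants who discontinued treatment prior to 12 weeks for any reason or were lost-to-follow up will be considered" non-responders. Protocol 8.7.8 has the same rule. Neither limits it by start date.

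On the excluded patients, Protocol 8.7.3 says "These patients will be included only in the analyses of the secondary and exploratory endpoints including safety", and SAP 3.3 repeats this. SAP 3.3 then says "All effectiveness analysis will be performed on the ITT population", and the protocol agrees: "All effectiveness analysis will be performed on ITT population". The modified ITT is built from the ITT. The Safety population needs only one dose.

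No calendar date for the end of abstraction appears in the supplied text. Protocol 8.9 says the study relies on records "available at the time of notification of the protocol to the French Data Hub", and Protocol 9.3 places that notification before study start.

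**The concern.** Potential follow-up is fixed by first dose and data cut. Treatment status at the cut arises after baseline and, under the non-responder rule, is part of the outcome. Suppose two patients start on the same late day. Under the exclusion sentence, the one who stopped stays in the denominator as a failure and the one who continued is removed. A late starter can then enter the primary proportion only as a failure. Under the opening ITT clause both are out. Two programmers could build different primary denominators from the same section.

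The second issue is the analysis set for the other effectiveness endpoints. Late starters still on drug are assigned to those analyses and also fall outside the only population on which effectiveness is to be run. The study is meant to support an FDA supplemental application, so both denominators should be unambiguous.

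**Working it through.** **No planned figure to reproduce.** The size of about 100 patients is practical, with no power calculation. As a method check only, the exact (Clopper-Pearson) interval for the 93/137 quoted in Protocol 6 comes out at 59.37% to 75.60%, as printed there.

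**Step 1: the rules applied to one patient.**

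| Patient starting less than 12 weeks before the cut | Opening ITT clause | Exclusion sentence plus non-responder rule |
|---|---|---|
| Still on drug | out | out |
| Stopped or lost before the cut | out | in, as non-responder |

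The conflict is confined to the second row.

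**Step 2: how many late starters.** Enrolment covers 5 April 2019 (ATU date, SAP 5.12) to 16 December 2022, which is 1351 days. Twelve weeks is 84 days, and 16 December 2022 + 84 days = 10 March 2023. Assuming uniform starts and 100 patients:

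- cut on 16 December 2022: 100 × 84/1351 = 6.2 late starters
- cut on 16 January 2023: 100 × 53/1351 = 3.9
- cut on 16 February 2023: 100 × 22/1351 = 1.6
- cut on or after 10 March 2023: 0

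**Step 3: effect on the primary proportion.** Let L be the late starters per 100, q the share of them who stopped or were lost before the cut, and p the response rate in patients with full potential follow-up. A start-date rule gives p. The second reading gives

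(100 − L)p / [(100 − L) + Lq].

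With L = 6:

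| p | q = 0.1 | q = 0.2 | q = 0.5 |
|---|---|---|---|
| 0.50 | 47/94.6 = 49.7% | 47/95.2 = 49.4% | 47/97 = 48.5% |
| 0.67 | 62.98/94.6 = 66.6% | 62.98/95.2 = 66.2% | 62.98/97 = 64.9% |

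The shift is −0.3 to −2.1 points. Over a wider assumed range (L = 3 to 12, p = 0.50 to 0.77, q = 0.1 to 0.5) it is −0.2 to −4.9 points. In whole patients, 63/94 = 67.0% (exact 95% CI 56.6 to 76.4) becomes 63/96 = 65.6% (55.2 to 75.0) when two late stoppers are kept as failures.

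**Step 4: secondary and exploratory effectiveness.** Late starters still on drug have under 12 weeks of follow-up, so they can contribute at Weeks 4 and 8. Because the Week 12 window is ±4 weeks, some with 8 to under 12 weeks on drug could also have an in-window Week 12 value. Week 24 and later tables are untouched. Safety is not in conflict.

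**The case against.** The strongest objection is that nobody may be affected. The first site opened on 16 December 2022, and Protocol v2.0, dated 18 April 2023, still describes abstraction in the future tense. In the ordinary sense, abstraction therefore ended after 10 March 2023 and there are no late starters. The undisplayed schematic may also give the date. This stands as a reason to call the effect possibly zero. It does not establish zero: Protocol 8.9 and 9.3 together allow a record cut at a notification made before study start, and the sponsor wrote a rule specifically for these patients.

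Second, uniform starts may overstate the number. SAP 1 says more than 50 patients with Cushing's syndrome (not restricted to non-CD) began before EU approval and commercialisation, which suggests earlier starts. The stopping share has no source in the documents. Both points stand; the figures are illustrations.

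Third, the exclusion sentence has a rationale. A patient who stopped has a determined outcome under the plan, and one still on drug does not. That is fair, but selecting on whether failure has already occurred is what lowers the proportion.

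Fourth, the excluded patients might remain in the ITT and leave only the primary analysis. The amendment table's rationale for Protocol 8.7.3 points that way, and it would remove the in/out conflict. The 12-week clause in the current ITT definition does not allow it. The On-Treatment population has no such clause, so on-treatment exploratory analyses can include these patients.

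A reader might infer more: that the plan firmly counts late stoppers as failures, or that the primary result is materially biased. The documents do not support either. The opening ITT clause already states the start-date rule, and the shift is small beside an exact interval of about ±10 points.

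**Conclusion.** The point holds as a contradiction to resolve. One clause makes membership of the primary denominator depend on start date; the exclusion sentence, with an unlimited non-responder rule, makes it depend on treatment status. If the second is programmed, the primary proportion is biased downward, against the drug, by about 0.3 to 2 points when about 6 of 100 patients are late starters. That range rests on assumed uniform starts, 10-50% stopping and a 50-67% response rate. It is zero if abstraction ended on or after 10 March 2023, which the supplied text neither confirms nor rules out. The conflict over secondary and exploratory effectiveness is explicit in both documents but reaches mainly the Week 4, Week 8 and possibly Week 12 tables. This is a minor point, worth settling because it fixes the primary denominator cheaply.

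**What to change.** Before database lock, and recorded in SAP 5.13:

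- State the end-of-abstraction date.
- Wherever the rule appears (SAP 3, 3.3 and 5.3.2; Protocol 8.1, 8.7.3 and 8.7.8), define the primary population as patients with a first dose at least 12 weeks before that date, whatever their treatment status on it. Within that population, keep patients who stopped or were lost before 12 weeks as non-responders. Editing only some of these sections would create new contradictions.
- Replace the sentence assigning all effectiveness analysis to the ITT: primary endpoint on the population above, secondary and exploratory effectiveness on all eligible treated patients.
- Say how the modified ITT follows from these sets.

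No new data are needed. The cost is that a few known failures may leave the denominator, so the reported rate can only stay the same or rise. The as-written version should therefore be reported alongside. The sponsor must judge whether this changes a principal feature under Protocol 8.7. If it does, an amendment is needed, with notification under Protocol 9.3.

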#### **Modified ITT Population**

This observational study is collecting data from an extended population of patients treated with osilodrostat in Cushing's syndrome in different conditions impacting in the study objectives. Therefore, to allow a better evaluation of the primary objective an additional population has been set.

The Modified ITT population consists of all participants as per the ITT excluding also the patients which for any reasons except for safety reasons did not collect the mean UFC at 12 weeks.

All effectiveness analyses will be performed on the modified ITT population as well.

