8.7.8 Analysis of Primary Endpoint

The number and proportion of patients with mean urinary free cortisol (mUFC) ≤ULN at 12 weeks will be summarised descriptively along with associated 95% CI. It is a fixed value, which is upper limit of normal range. The patients who discontinued treatment prior to 12 weeks for any reason or were lost-to-follow up will be considered non-responders for the primary endpoint. The patients who started treatment with osilodrostat less than 12 weeks prior to the end of the abstraction period, and are still treated with osilodrostat at the end of the abstraction period will be excluded from the analysis.

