#### Modified ITT (mITT) Patient Identification Data Review Process

- Step 1. Statistical programmer programs to create excel file, which is a list of patients who will be excluded from ITT population due to lack of mUFC data at week 12. Send this excel file to DML.
- Step 2. Based on the list of patients in above excel file, DM team will track all the possible reasons why patients did not have mUFC data at week 12 for each patient.
- Step 3. Get the information of reasons for no mUFC data at week 12 from DML, draft data review report.
- Step 4. Send the drafted data review report to Recordati for review.
- Step 5. Get the review comments from Recordati, discuss the review comments in comments resolution meeting.

The above data review process will also be applied to the missing mUFC data at the baseline.

Project Document Version No.: 4.0; Document Effective Date: 30 October 2023

CONFIDENTIAL

TP-GDO-WW-096-09 Effective Date: 22 Dec 21

Related to: SOP-GDO-WW-019 Page 14 of 31

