#### **Safety Population**

The Safety population consists of all participants who receive at least one dose of osilodrostat.

Safety analysis will be performed on the Safety population.

Decisions regarding the exclusion of participants and/or participant data from analyses will be made prior to the Database lock (DBL) during the data review meeting and will be documented and approved by Recordati.

The number and percentage of patients included and excluded from each analysis population, along with reasons for exclusion, will be summarized.

A listing of participants included in each analysis population will also be provided. Participants exclusion from analysis sets will be listed with reasons for exclusions.

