# RECORDATI AG, Rare Diseases Branch LCI699-RECAG-NI-0596

Statistical Analysis Plan

The primary endpoint will be evaluated also on the modified ITT population, in which participants who had any intervention for any reason or condition that would not allow to have a mean UFC evaluation at 12 weeks will be excluded from the analysis. Participants who discontinued prior to 12 weeks due to safety reasons will be considered non -responders.

The summary statistics will include sample size, frequency, percentages, and 95% CI for proportion.

A participant level listing of participants with mUFC will be provided with UFC, ULN, date of assessment, lost to follow up date etc.

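### SAP 5.10 gives Week 12 mUFC response by subgroup only for the mITT and On-Treatment populations, so no planned subgroup rate counts non-safety early stops and losses as non-responders (minor)

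*SAP*

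**What the plan says.** **ITT rule.** SAP 5.3.2 states: "The participants who discontinued treatment prior to 12 weeks for any reason or were lost-to-follow up will be considered non-responders for the primary endpoint". Protocol 8.7.8 has the same rule. SAP 3.3 adds: "All effectiveness analysis will be performed on the ITT population".

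**mITT rule.** SAP 3.3 forms the mITT from the ITT, "excluding also the patients which for any reasons except for safety reasons did not collect the mean UFC at 12 weeks". It says effectiveness analyses will be run on the mITT as well, so the mITT is additional. SAP 5.3.2 words the exclusion differently, removing "participants who had any intervention for any reason or condition that would not allow to have a mean UFC evaluation at 12 weeks". On safety stops it says "Participants who discontinued prior to 12 weeks due to safety reasons will be considered" non-responders. The term for safety reasons is not defined.

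**On-Treatment.** SAP 3.3 limits this population to participants while they are taking osilodrostat at the timepoint or period concerned.

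**Subgroups.** SAP 3.5 defines four families: type of intervention, method of use or titration, reason for use, and type of non-CD Cushing's syndrome. All five efficacy items in SAP 5.10 ii name the mITT and On-Treatment populations. None names the ITT. The one comparison by group assigned to the ITT is the test by other Cushing's therapy in SAP 5.3.6, which is not a 3.5 subgroup.

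**Traceability.** For the mITT, SAP 3.3 says the "DM team will track all the possible reasons why patients did not have mUFC data at week 12". It also says: "Decisions regarding the exclusion of participants and/or participant data from analyses will be made prior to the Database lock (DBL"). SAP 5.10 i includes patient disposition by subgroup, and SAP 5.4 defines disposition to include premature discontinuation by reason.

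**The concern.** A patient who stops before Week 12 for a non-safety reason, or is lost, and has no mUFC in the Week 12 window (±4 weeks, so Weeks 8 to 16) is a failure in the ITT and absent from the mITT. As worded, this can include a stop for lack of effect or a switch of treatment. The On-Treatment population leaves the same patients out. Overall this does little harm, because the ITT and mITT rates will both be reported and the difference can be seen. By subgroup, the ITT rate is not on the list of outputs.

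Two things follow if such patients exist. Each subgroup rate is higher than its ITT counterpart. Subgroups that lose different fractions of patients can also appear to differ when their ITT rates are equal. The protocol says the study supports a proposed label covering all forms of endogenous Cushing's syndrome, so rates by aetiology may well be read; that last step is an inference.

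**Working it through.** **Plan figures.** The documents give no expected response rate, subgroup sizes or number of patients without a Week 12 mUFC. The sample size is about 100 on practical grounds. There is no plan figure to reproduce on this point. As a check of the interval method only (exact Clopper-Pearson, SAP 5.2), the 93/137 that the protocol cites from an earlier trial gives 67.9% (59.37 to 75.60), as printed there.

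**Who is counted at Week 12**

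| Patient | ITT | mITT | On-Treatment |
|---|---|---|---|
| Safety stop before Week 12 | non-responder | non-responder | not included |
| Non-safety stop or loss, no value in Weeks 8 to 16 | non-responder | excluded | not included once off drug |
| Non-safety stop, value in Weeks 8 to 16 | non-responder | kept; rule not restated | not included once off drug |
| Still on drug, no Week 12 test | no rule stated | excluded | included, no value |

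The second row carries the point. The last row is a separate gap: SAP 5.3.2 gives no rule for these patients and SAP 5.11.1 replaces no missing data. They are not part of k below.

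**Formula.** Let N be the ITT number, R the responders, and k the second-row patients. The ITT rate is R/N and the mITT rate is R/(N-k). Their ratio is N/(N-k). With R fixed, the mITT rate cannot be lower than the ITT rate.

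**Illustrations (all N, R and k are assumptions; 95% exact CIs)**

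- Overall, 40/100 = 40.0% (30.3 to 50.3):
  - k = 10: 40/90 = 44.4% (34.0 to 55.3), ratio 100/90 = 1.111.
  - k = 20: 40/80 = 50.0% (38.6 to 61.4), ratio 1.25.
- Subgroup of 25, 10/25 = 40.0% (21.1 to 61.3):
  - k = 3: 10/22 = 45.5% (24.4 to 67.8), ratio 25/22 = 1.136.
  - k = 5: 10/20 = 50.0% (27.2 to 72.8).
- Smallest k for a rise of at least 5 points from 40%: 12 of 100 (40/88 = 45.5%), but 3 of 25.
- Unequal exclusion in two subgroups with the same ITT rate of 10/25: losing 1 gives 10/24 = 41.7% and losing 5 gives 10/20 = 50.0%. The 8.3-point difference comes from exclusion alone.

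Each of these shifted rates lies inside its own ITT interval. That depends on the inputs. A deliberately heavy case, 20 of 50 removed from 20/50 = 40.0% (26.4 to 54.8), gives 20/30 = 66.7%, which is outside. Nothing in the documents says that exclusion will be that heavy.

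**Short-term use.** Under the ITT rule, patients who permanently stopped before Week 12 for surgery are non-responders whatever their mUFC. If the under-12-weeks definition in SAP 3.5 means a permanent stop before calendar Week 12, this subgroup has an ITT rate of 0% by rule. SAP 5.9.5 assesses interrupted treatment case by case, so that reading is not certain for every patient.

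**The case against.** The strongest reply is that the ITT is already the default and the mITT is only additional. On that view 5.10 ii, which calls its items selected, is just an incomplete list. This is a fair reading, and it makes the matter one of reconciliation. But someone programming from the specific list would produce no ITT subgroup table.

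A reader might infer that early failures will be hidden by subgroup. The documents do not support that. Disposition by subgroup shows stops by reason, exclusions are listed with reasons, and a participant listing of mUFC is planned. Much of the effect could be reconstructed. What is missing is the ITT rate itself.

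It can also be said that the ITT is not the truth either: counting a planned surgical stop as drug failure may understate the drug's effect. That stands. It is why the ITT rate belongs beside the mITT rate with a footnote, and does not replace it.

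A reader might go further and hold that the mITT should be rebuilt around a closed list of permitted exclusions. Doing so would bring it close to the ITT and defeat the purpose SAP 3.3 gives for it, which is to allow for patients treated in differing conditions. Once the ITT tables exist, that step is not needed.

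Finally, one might suppose that an early stop with an in-window value could become an mITT responder. The natural reading is otherwise. SAP 5.3.2 evaluates the same primary endpoint on the mITT, and the any-reason non-responder rule is attached to that endpoint. Likewise, the first step of the mITT review identifies patients by lack of Week 12 mUFC data, which largely settles the two wordings. Both need confirming, and neither is a demonstrated error.

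**Conclusion.** The point holds at subgroup level and is minor. SAP 5.10 ii does not carry through the ITT default in SAP 3.3, so no planned Week 12 response rate by the 3.5 subgroups applies the non-responder rule to non-safety early stops and losses. The direction is known, given at least one such patient and an unchanged number of responders: the subgroup mITT rate exceeds the ITT rate by the factor N/(N-k). The size cannot be derived from the documents.

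It would be wrong to conclude that the overall primary result is inflated. That result is on the ITT with the stricter rule, and it is unaffected. The subgroup tables are descriptive. The contrast is firm only at Week 12, because the non-responder rule is written for the primary endpoint and not for the other visits.

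**What to change.** 1. In SAP 5.10 ii, add the ITT to the Week 12 mUFC response item for each 3.5 subgroup, using the non-responder rule of 5.3.2, beside the mITT and On-Treatment results. Footnote that short-term-use patients who permanently stopped before Week 12 are non-responders by rule. Other visits and the change-from-baseline items need not change.
2. Use one mITT wording in SAP 3.3 and 5.3.2, and state before database lock what safety reasons cover, including where a stop or death from disease progression falls.
3. Confirm in 5.3.2 that the any-reason non-responder rule also applies in the mITT to early stops with a value in the Week 12 window.

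The mITT itself need not be redefined. The cost is a few lines of SAP text and up to four descriptive tables, one per subgroup family. No new data are needed. The downside is slightly longer output, with lower percentages shown beside the mITT figures.
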